4.3.3. Patient-Reported Outcomes

PRO endpoints will be obtained at Day 0 prior to first dose, Weeks 4, 12, 24 after dosing, and at Weeks 15, 27, 48, 52, 74, and Weeks 96, and 100 as applicable.

For the SF-36 results, scores and changes from baseline for the 8 subscales (Physical Functioning, Role Physical, Bodily Pain, General Health, Vitality, Social Functioning, Role Emotional and Mental Health) as well as the Physical Component Summary (PCS) and Mental Component Summary (MCS) will be summarized using medians and associated exact non-parametric 95% CIs by treatment group.

For the EQ-5D-5L results, the assessment of 5 health categories (1-5 scales) and overall health score, "Your Health Today", (1-100 scale) will be summarized; the scores and changes from baseline will be summarized using medians and associated exact non-parametric 95% CIs, by treatment group.

For the WOMAN-PRO results, 31 self-reported items assessing physical and psychosocial impacts will be summarized. Scores and change from baseline will be summarized for the group of 15 wound-related domain items and the group of 5 difficulties in daily life domain items, the group of 11 psychosocial domain items, and each of the 31 individual items. Medians and associated exact non-parametric 95% CIs will be constructed, by treatment group.

For the 2 additional Global PRO questions assessing quality of life after surgery or biopsy, the time outcome will be summarized with a median and associated exact non-parametric 95% CI, and the binary yes/no outcomes will be summarized with a proportion and associated exact Clopper-Pearson 95% CI, by treatment group.

All PRO data will be presented by study visit in data listings.

| Table 14.2.3.1 | Summary of SF-36 Outcomes by Visit (mITT Population) |
|----------------|-------------------------------------------------------------|
| Table 14.2.3.2 | Summary of EQ-5D-5L Outcomes by Visit (mITT Population) |
| Table 14.2.3.3 | Summary of WOMAN-PRO Outcomes by Visit (mITT Population) |
| Table 14.2.3.4 | Summary of Global PRO Outcomes at Week 52 (mITT Population) |
| | |

| Listing 16.2.9.5 | Patient Reported Outcomes: SF-36 Results |
|------------------|----------------------------------------------|
| Listing 16.2.9.6 | Patient Reported Outcomes: EQ-5D-5L Results |
| Listing 16.2.9.7 | Patient Reported Outcomes: WOMAN-PRO Results |
| Listing 16.2.9.8 | Global PRO Results |

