1.1.3.3. Exploratory Objectives

The exploratory objectives include the following:

- To describe the efficacy of VGX-3100, administered alone or in combination with imiquimod, at Week 74 and/or Week 96 as measured by reduction in the surface area of the qualifying vulvar lesion(s), in subjects without a complete lesion resolution at Week 48
- To describe the long term efficacy of VGX-3100, alone or in combination with prior imiquimod, as measured by histologic regression of vulvar HSIL
- To describe the long term efficacy of VGX-3100, alone or in combination with prior imiquimod, as measured by virologic clearance of HPV-16/18
- To evaluate tissue immune responses to VGX-3100, and VGX-3100 with imiquimod, as measured in vulvar tissue samples
- To describe virologic clearance of HPV-16/18 from non-vulvar anatomic locations
- To describe association of microRNA (miRNA) profile, previous vulvoscopy, and HPV testing results with Week 48 histologic regression
- To describe patient reported outcomes (PRO) for subjects treated with VGX-3100 and VGX-3100 with imiquimod
- To describe the humoral and cellular immune response of VGX-3100 administered alone or in combination with imiquimod, post dose 3, post dose 4, and after additional dosing
- To determine the long term efficacy of VGX-3100 alone or in combination with imiquimod with respect to histopathologic regression of vulvar HSIL or virologic clearance of HPV-16/18 in vulvar tissue

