3.2. General Methods

All data listings that contain an evaluation date will contain a relative study day (Rel Day). Pretreatment and on-treatment study days are numbered relative to the day of the first dose of study medication (Day 0) which is designated as Rel Day 1. The preceding day is Rel Day -1, the day before that is Rel Day -2, etc. There is no Rel Day 0.

All output will be incorporated into Microsoft Word or Excel files, or Adobe Acrobat PDF files, sorted and labeled according to the International Conference on Harmonisation (ICH) recommendations, and formatted to the appropriate page size(s).

Tabulations will be produced for appropriate demographic, baseline, efficacy, immunogenicity, and safety parameters. For categorical variables, summary tabulations of the number and percentage of subjects within each category of the parameter will be presented. For continuous variables, the number of subjects, mean, median, standard deviation (SD), minimum, and maximum values will be presented. Summarizations will be presented by treatment grouping and overall as applicable.

Formal statistical hypothesis testing will be performed on the primary endpoint for each treatment group compared to historical control separately at a 1-sided, 0.025 level of significance. Summary statistics will be presented, as well as 2-sided 95% confidence intervals (CIs) on selected efficacy and safety parameters, as described in the sections below.

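### For single PRO items, Section 4.3.3 names only the median change and its exact CI, which shows little of how many subjects improved or worsened; counts of improved, unchanged and worsened should be added

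*SAP*

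**What the plan says.** SAP Section 4.3.3 sets the PRO summaries. For EQ-5D-5L it covers "the assessment of 5 health categories (1-5 scales) and overall health score", and states that "scores and changes from baseline will be summarized using medians and associated exact non-parametric 95% CIs, by treatment group". For WOMAN-PRO it covers three domain groups (15, 5 and 11 items), ending with "the group of 11 psychosocial domain items, and each of the 31 individual items", and then says: "Medians and associated exact non-parametric 95% CIs will be constructed, by treatment group". The section names no other statistic for these single items. The SAP does not state the response scale of the WOMAN-PRO items.

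The objective these tables serve is in Section 1.1.3.3: "To describe patient reported outcomes (PRO) for subjects treated with VGX-3100 and VGX-3100 with imiquimod".

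Section 3.2 gives general defaults for tabulations. For categorical data: "For categorical variables, summary tabulations of the number and percentage of subjects within each category of the parameter will be presented". For continuous data: "For continuous variables, the number of subjects, mean, median, standard deviation (SD), minimum, and maximum values will be presented". The SAP does not say which type a 1-5 item is, or whether Section 4.3.3 adds to these defaults or replaces them.

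**The concern.** The median suits a score with many possible values, such as the SF-36 scales or the overall health score. A single item with a handful of levels is different. Its change from baseline takes a few integer values, and 0 is likely to be common. The median of such data can stand only on one of those integers, or midway between two, and the ends of its exact interval are themselves observed integers. Most of what the item records, namely how many women improved, how many worsened and how many did not move, does not reach the table.

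This affects 5 + 31 = 36 items per arm, at up to 10 post-baseline visits. If the item tables are to describe PROs in each arm, they should let a reader see whether a quarter or three quarters of the women changed. Worsening matters as much as improvement here, since one arm applies a topical agent to the lesion for 20 weeks.

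**Working it through.** The SAP states no figure for the PROs, so there is none to reproduce. The check asks what the planned statistic can show.

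**Inputs from the SAP.** Arms of 24 and 12 (Section 1.2.1) and 90% evaluable at Week 48 (Section 3.1): 0.9 × 24 = 21.6 and 0.9 × 12 = 10.8, taken as 22 and 11.

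**Assumptions.** The 90% figure carries over to PRO visits; item changes are -1, 0 or +1, with -1 for improvement; WOMAN-PRO items are coarse ordinal; the shift rates are illustrative.

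**Exact interval.** The non-parametric 95% CI for a median runs from the k-th to the (n+1-k)-th ordered value. Its coverage is 1 - 2·P(Bin(n, ½) ≤ k-1), and k is the largest value that keeps coverage at or above 95%.
- n = 22: k = 6, so 6th to 17th value, coverage 98.3% (k = 7 would give 94.8%).
- n = 11: k = 2, so 2nd to 10th value, coverage 98.8% (k = 3 would give 93.5%).

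**What is printed when m subjects improve one level and nobody worsens.** The lower limit becomes -1 when m ≥ k, and the upper limit becomes -1 when m ≥ n+1-k.

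| n | Improvers m | Median change | Exact CI |
|---|---|---|---|
| 22 | 0-5 | 0 | (0, 0) |
| 22 | 6-10 | 0 | (-1, 0) |
| 22 | 11 | -0.5 | (-1, 0) |
| 22 | 12-16 | -1 | (-1, 0) |
| 22 | 17-22 | -1 | (-1, -1) |
| 11 | 0-1 | 0 | (0, 0) |
| 11 | 2-5 | 0 | (-1, 0) |
| 11 | 6-9 | -1 | (-1, 0) |
| 11 | 10-11 | -1 | (-1, -1) |

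The same interval therefore covers 6/22 = 27% to 16/22 = 73% improved, and 2/11 = 18% to 9/11 = 82%. Within that range the point estimate tells only on which side of one half the proportion lies. With the sign reversed, the table holds for worsening.

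**How often the median is 0.** With so few worsening, this is essentially P(at most 10 of 22 improve) or P(at most 5 of 11 improve).
- 40% improved, 5% worsened: P(Bin(22, 0.4) ≤ 10) = 77%; P(Bin(11, 0.4) ≤ 5) = 75%.
- 50% improved, 5% worsened: 42% and 50%.
- 60% improved, 5% worsened: 12% and 25%.

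In the 40%/5% case the interval is (-1, 0) in 93% (n = 22) and 87% (n = 11) of samples, and (0, 0) in 7% and 2%. At n = 11 nearly all the rest read (-1, 1).

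**The same data with counts.**
- 6 of 22 improved: planned output 0 (-1, 0); proportion 27%, Clopper-Pearson 11% to 50%.
- 9 of 22 improved: planned output 0 (-1, 0); proportion 41%, 21% to 64%.
- 16 of 22 improved: planned output -1 (-1, 0); proportion 73%, 50% to 89% (the complement of 6 of 22).
- 4 of 11 improved: planned output 0 (-1, 0); proportion 36%, 11% to 69%.

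**The case against.** **Section 3.2 may already supply more.** It sets defaults for efficacy tabulations, and the PROs sit under Section 4.3, Efficacy Evaluation. If an item is treated as continuous, a mean and SD would appear; if categorical, the percentage at each level. The table shells, in a separate document, may settle this. The objection stands in part: it cannot be said that only the median will be reported. But the SAP does not say that the defaults apply to these items, and neither default as written asks for counts of improved and worsened subjects. Level percentages at a visit do not show who moved.

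**A reader might infer that the exact CI stays at 0, so that real shifts are reported as no change.** The calculation does not support that. One limit moves to -1 once 6 of 22 or 2 of 11 improve, so a shift in 40% of women would usually print as 0 (-1, 0). That hints at direction but not at extent.

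**A reader might also infer a loss of power, because the median CI rarely excludes 0.** That is not a fair test. If 40% improve and 55% are unchanged, the true median change is 0 and an interval containing 0 is correct. Section 3.2 places formal testing on the primary endpoint, and excluding 0 is not a criterion for the PROs.

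**The information is not lost.** All PRO data are listed by visit, and the WOMAN-PRO domain groups, overall health score and SF-36 scales are summarised too. A median for ordinal data is also defensible. These points stand; they limit the severity and argue for adding to the median rather than replacing it.

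**Conclusion.** The point holds as a low-severity improvement. For single coarse items, the one summary that Section 4.3.3 names gives an interval of (-1, 0) across roughly 27% to 73% improved in the larger arm and 18% to 82% in the smaller, with a point estimate that shows only which side of one half the proportion falls. When 40% improve and 5% worsen, the median change is 0 in about three quarters of samples. At 50% or 60% improved a zero median is much less common, so the item tables would not be uniformly uninformative.

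The numbers rest on 22 and 11 evaluable subjects, one-level changes and illustrative shift rates. For EQ-5D-5L the 1-5 scale is stated. For the 31 WOMAN-PRO items a coarse scale is assumed, and the point weakens if their scale is fine. The SF-36 scales, overall health score and WOMAN-PRO domain scores are outside this criticism.

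**What to change.** In Section 4.3.3, keep the median and its exact CI. For the five EQ-5D-5L categories and the individual WOMAN-PRO items, add the number and percentage of subjects improved, unchanged and worsened from baseline at each visit, by treatment group, with exact Clopper-Pearson 95% CIs. Show these in Tables 14.2.3.2 and 14.2.3.3. State also whether the Section 3.2 defaults apply to single items. A mean change is optional; it treats the levels as equally spaced, which the counts do not.

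The cost is a few sentences in the SAP, extra rows in two tables and a matching change to the shells. No new data are needed, and Section 4.3.3 already uses Clopper-Pearson intervals for the yes/no PRO outcomes. The downside is longer tables.

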4.3.4. Immunology Endpoints

The following immunology endpoints will be presented in tabulations:

- ELISpot results will be presented by treatment group and scheduled visit, and increase from baseline will be analyzed using an exact non-parametric 95% CI on the median at each time point after baseline (Weeks 15, 27, 48, 74, and 96).
- HPV-16 and HPV-18 E7 specific ELISA results will be presented by treatment group and scheduled visit and analyzed using an exact non-parametric 95% CI on the median at each time point after baseline (Weeks 15, 27, 48, 74, and 96).
- Increase from baseline in frequency of VGX-3100 specific CD8+/CD137+ PBMCs that are Perforin+ will be presented by treatment group and will be analyzed using an exact non-parametric 95% CI on the median.
- Change from baseline in pro-inflammatory and immunosuppressive elements in vulvar tissue, which may include visualization of PD-L1, Granulysin, perforin, CD137, CD103, and possibly other relevant markers, will be presented by treatment group and will be analyzed using a t-distribution based 95% CI on the mean.

All immunology data will be presented by study visit in data listings.

| Table 14.2.4.1A | ELISpot Results by Treatment Group and Scheduled Visit (mITT Population) |
|-----------------|---------------------------------------------------------------------------------------------------------------------------------------------------------|
| Table 14.2.4.1B | ELISpot Results by Treatment Group and Scheduled Visit (PP Population) |
| Table 14.2.4.2A | HPV-16 and HPV-18 E7 Specific ELISA Results by Treatment Group and Scheduled Visit (mITT Population) |
| Table 14.2.4.2B | HPV-16 and HPV-18 E7 Specific ELISA Results by Treatment Group and Scheduled Visit (PP Population) |
| Table 14.2.4.3A | Increase from Baseline in Frequency of VGX-3100 Specific CD8+/CD137+ PBMCs that are Perforin+ by Treatment Group (mITT Population) |
| Table 14.2.4.3B | Increase from Baseline in Frequency of VGX-3100 Specific CD8+/CD137+ PBMCs that are Perforin+ by Treatment Group (PP Population) |
| Table 14.2.4.4A | Change from Baseline in Pro-inflammatory and Immunosuppressive Elements in Vulvar Tissue by Treatment Group and Scheduled Visit (mITT Population) |

| Table 14.2.4.4B | Change from Baseline in Pro-inflammatory and Immunosuppressive | |
|-------------------|----------------------------------------------------------------------|--|
| | Elements in Vulvar Tissue by Treatment Group and Scheduled Visit (PP | |
| | Population) | |
| Listing 16.2.6.7 | Immunologic Assay Collection | |
| Listing 16.2.6.8A | Immunologic Results: ELISA and ELISpot | |
| Listing 16.2.6.8B | Immunologic Results: Flow Cytometry | |
| Listing 16.2.6.8C | Immunologic Results: Pro-inflammatory and Immunosuppressive | |
| | Elements in Vulvar Tissue | |

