Subjects in Subgroups C and D may receive a fifth and possibly a sixth dose at Week 52 and Week 78, respectively.

To assess quality of life and related impacts on subjects, PRO instruments will be provided and will include the Short Form Health Survey version 2 (SF-36v2TM), the EQ-5D-5L (EuroQol Research Foundation), WOMAN-PRO (WOMen with vulvAr Neoplasia) Clinical Trial Version 2.0, and 2 additional PRO questions assessing quality of life after surgery or biopsy.

The total duration of the study is up to 10 weeks for the screening period and up to100 weeks for the treatment and follow-up periods. The study duration is reduced to 78 weeks for subjects that have not already completed the Week 78 visit.

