3.8. Subpopulations

Certain subgroups will be analyzed separately at additional time points for effectiveness of additional doses and/or surgical treatments.

- Subgroups A and B Subjects with no HSIL at Week 48 will receive 4 doses.
- Subgroups C and D Subjects with HSIL at Week 48, who have a reduction in lesion size or no increase in lesion size from baseline, may receive a fifth dose of VGX-3100 administered IM with EP at Week 52 per the judgment of the Investigator. Subjects with HSIL at Week 74 may receive a sixth dose of VGX-3100 administered IM with EP at Week 78 per the judgment of the Investigator.
- Subgroup E Subjects may receive surgical treatment per the judgment of the Investigator.

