4.3.2. Secondary and Exploratory Efficacy Endpoints

Secondary and exploratory efficacy endpoints are supportive to the primary hypothesis.

The following secondary and exploratory efficacy binary endpoints will be presented as percentage point estimates and exact Clopper-Pearson 95% CIs. Each of the following endpoints will be analyzed separately based on qualifying lesions present at baseline and for all lesions regardless of presence at baseline, unless otherwise noted.

- Histologic regression of vulvar HSIL or virologic clearance of HPV-16/18 in vulvar tissue will be assessed at Weeks 74 and 96 by treatment group for all subjects and stratified by subjects who receive 4 or 5 doses (Week 74) and 4, 5, or 6 doses (Week 96).
- Histologic regression of vulvar HSIL will be assessed at Week 48 by treatment group.
- Virologic clearance of HPV-16/18 in vulvar tissue will be assessed at Week 48 by treatment group.
- Histologic regression of vulvar HSIL will be assessed at Weeks 74 and 96 by treatment group for all subjects and stratified by subjects who receive 4 or 5 doses (Week 74) and 4, 5, or 6 doses (Week 96).
- Virologic clearance of HPV-16/18 in vulvar tissue will be assessed at Weeks 74 and 96 by treatment group for all subjects and stratified by subjects who receive 4 or 5 doses (Week 74) and 4, 5, or 6 doses (Week 96).
- Histologic regression of vulvar HSIL to normal tissue will be assessed at Week 48 by treatment group. Normal tissue is defined as having no evidence of vulvar HSIL, no evidence of LSIL (VIN1), and no evidence of condyloma.
- Non-progression of vulvar HSIL to vulvar cancer will be investigated at Week 48 by treatment group. Progression is defined as advancement to carcinoma by histology according to the Pathology Adjudication Committee.
- Virologic clearance of HPV-16/18 outside of the vulva will be assessed at Week 48 by treatment group (for qualifying lesions only) and be presented by anatomic location (cervical, intra anal, oral, and vaginal).
- Histologic regression of vulvar HSIL or virologic clearance of HPV-16/18 in vulvar tissue will be assessed at Weeks 48, 74, and 96 by treatment group.

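### Week 74 and Week 96 ELISpot and ELISA tables pool subjects with different numbers of doses, so they do not answer the exploratory objective on the response after additional dosing

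*SAP*

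**What the plan says.** **Objective.** SAP 1.1.3.3 includes an exploratory objective to describe humoral and cellular responses at three stages: "post dose 3, post dose 4, and after additional dosing".

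**Who is re-dosed.** SAP 1.2.1: "Subjects in Subgroups C and D may receive a fifth and possibly a sixth dose at Week 52 and Week 78, respectively". For Subgroups A and B, SAP 3.8 says: "Subjects with no HSIL at Week 48 will receive 4 doses". A footnote to Table 1-1 adds that, after Amendment 5.0, partial responders reaching Week 78 are no longer offered dose 6.

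**Who is sampled.** Table 1-1 marks blood immunology samples at Weeks 74 and 96 without limiting them to re-dosed subjects.

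**Immunology analysis.** SAP 4.3.4 says: "ELISpot results will be presented by treatment group and scheduled visit". It also says: "HPV-16 and HPV-18 E7 specific ELISA results will be presented by treatment group and scheduled visit". The statistic is an "exact non-parametric 95% CI on the median at each time point after baseline (Weeks 15, 27, 48, 74, and 96"). The table titles use the same two classifiers, for example "ELISpot Results by Treatment Group and Scheduled Visit (mITT Population").

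**Efficacy analysis at the same weeks.** In SAP 4.3.2, regression and clearance are presented for all subjects and also "stratified by subjects who receive 4 or 5 doses (Week 74) and 4, 5, or 6 doses (Week 96").

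**The concern.** Up to Week 48, visit works as a label for dosing stage: Week 15 follows dose 3 and Week 27 follows dose 4 for everyone on schedule. After Week 52 it does not, because two subjects in the same arm at the same visit may have had different numbers of doses. A median by arm and visit then describes a mixture, in proportions the SAP does not give.

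A reader of the Week 74 or Week 96 row could see a small change and conclude that extra doses do little, when the figure is diluted by subjects who had none. Waning in 4-dose subjects could likewise be taken for failure of the extra dose. What is at stake is an exploratory description, not the primary conclusion. The SAP recognises the same problem for efficacy and leaves it open for the endpoint whose objective explicitly mentions extra dosing.

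**Working it through.** No figure in the SAP is contested, so there is none to reproduce. The check compares the sections and then sizes the dilution under stated assumptions.

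**1. Dose histories present at each visit**

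| Visit | Possible extra doses by then | Dose counts pooled (subjects with at least 4) | Split in 4.3.2 | Split in 4.3.4 |
|---|---|---|---|---|
| Week 74 | dose 5 at Week 52 | 4, 5 | 4 or 5 | none |
| Week 96 | dose 5 at Week 52, dose 6 at Week 78 | 4, 5, 6 | 4, 5 or 6 | none |

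The 4.3.2 split shows that 4-dose subjects are expected at both visits. The mITT population (2.1) can also contain subjects with fewer than 4 doses.

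**2. Dilution of the pooled median**

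Assumptions, none of them from the SAP: log-normal response levels with log-SD 1; 4-dose subjects have median 1; a fraction f is re-dosed and has median 5. The pooled median is exp(m), where m solves

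(1 − f)·Φ(m) + f·Φ(m − ln 5) = 0.5, with ln 5 = 1.609.

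Example, f = 0.20: m = 0.261 gives 0.80 × 0.603 + 0.20 × 0.089 = 0.482 + 0.018 = 0.500, so the pooled median is exp(0.261) = 1.30. At f = 0.50 the mixture is symmetric on the log scale, so the answer is √5 = 2.24, which confirms the formula.

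| Re-dosed fraction f | Pooled median for a true 5-fold boost |
|---|---|
| 20% | 1.30 |
| 33% | 1.61 |
| 50% | 2.24 |
| 60% | 2.73 |
| 72% | 3.39 |

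The range reaches 72% because SAP 3.1 assumes that 20% and 28% meet the combined endpoint, leaving 80% and 72% who do not. Not all of those are candidates for re-dosing: some fail on HPV alone, some fall in Subgroup E, and extra dosing is at the investigator's judgment.

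**3. Same point on the change scale**

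ELISpot is analysed as increase from baseline, so a second illustration uses changes. With 90% evaluable (3.1), the arms of 24 and 12 give 21.6 and 10.8, taken as 22 and 11. Let 4-dose subjects have change 0 and re-dosed subjects change 1. With 22 subjects the pooled median is 0 for up to 10 re-dosed, 0.5 at 11 and 1 at 12. With 11 subjects it is 0 for up to 5 and 1 from 6. The pooled value thus depends on how many were re-dosed as well as on how they responded.

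**4. What a split table can support**

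The widest order-statistic interval for a median has coverage 1 − 2 × 0.5ⁿ.

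- n = 5: 1 − 2 × 0.03125 = 93.75%, short of 95%.
- n = 6: 1 − 2 × 0.015625 = 96.88%.

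An exact 95% interval therefore needs at least 6 subjects in the cell. With 12 subjects planned for the imiquimod arm, some cells will probably fall below that.

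**The case against.** **The objective can be met from other planned output.** It is exploratory and descriptive, and about 36 subjects are enrolled. Listings of immunology results (16.2.6.8A), dosing (16.2.5.1) and subgroup status (16.2.3.3) would let a reader rebuild the dose groups. This is true and limits the importance of the point. But 4.3.4 says these endpoints are tabulated, and a join left to the reader is not a prespecified summary.

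**Section 3.8 already promises separate subgroup analyses.** It does so for the effectiveness of additional doses and names no immunology analysis. No listed immunology table carries a dose stratum. The table shells are in a separate document that is not shown, so their layout is unknown, but the SAP text does not call for a split.

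**A majority may be re-dosed.** A reader might infer that the pooled median mainly reflects 4-dose subjects and so hides any boost. The SAP does not support that: it gives no re-dosed fraction, and its response assumptions are compatible with more than half. Above one half the pooled median leans towards re-dosed subjects. What stands is dilution, strong or moderate depending on the fraction.

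**Little Week 96 data may exist.** Amendment 5.0 ends the offer of dose 6 for later subjects, and 1.2.1 shortens the study to 78 weeks for those who had not completed that visit. This stands; Week 74 is where the split matters most.

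**Timing also limits the answer.** Week 74 is 74 − 52 = 22 weeks after dose 5 and Week 96 is 96 − 78 = 18 weeks after dose 6, against 3 weeks for Weeks 15 and 27. A short-lived boost could be missed even in split tables. This stands, and the split does not cure it.

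**Conclusion.** The point holds as a mismatch between an exploratory objective and its planned tables. Under 4.3.4 as written, Week 74 mixes 4 and 5 doses and Week 96 mixes 4, 5 and 6, so the response after additional dosing cannot be read from either.

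Under the log-normal assumption (log-SD 1), a true 5-fold boost appears as roughly 1.3-fold to 3.4-fold over re-dosed fractions of 20% to 72%. It is diluted throughout, but not always masked. These figures model response levels and only illustrate the planned ELISpot statistic, which is an increase from baseline.

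Two stronger readings are not supported. Week 74 cannot contain 6-dose subjects, because dose 6 is given at Week 78. And a split by doses would not estimate the effect of an extra dose: re-dosing depends on HSIL and lesion status at Week 48, so the groups differ in more than dose count. The issue is minor; it touches neither the primary endpoint nor its test.

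**What to change.** In SAP 4.3.4 and Tables 14.2.4.1A/B and 14.2.4.2A/B:

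- Present Week 74 ELISpot and ELISA by 4 or 5 doses received and Week 96 by 4, 5 or 6, within treatment group, as in 4.3.2. State where mITT subjects with fewer than 4 doses are shown.
- For re-dosed subjects, add the within-subject change from Week 48, the last scheduled sample before dose 5.
- Give the exact non-parametric 95% interval for the median only in cells of at least 6 subjects. In smaller cells show the median, range and individual values.
- Label the split descriptive because re-dosing depends on Week 48 status, and note that Week 96 and 6-dose cells may be sparse or empty after Amendment 5.0.

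The cost is SAP wording and extra columns in existing tables. The samples are already scheduled and no visit or treatment changes. The drawback is small cells in exploratory tables, which 4.3.2 already accepts for efficacy.
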